#### **Glycemic Guidelines during Research Visit**

1. Upon arrival, the subject will be asked to check the CGM reading and ketone concentration using the study ketone meter. If CGM <70 mg/dL or >300 mg/dL or ketone test is >0.6 mmol/L, study physician will suggest appropriate treatment. The study subject may continue participation in the trial once CGM is between 70-300 mg/dL and ketone concentration ≤0.6 mmol/L.
2. If CGM >300 mg/dL for more than 1 hour or >400 mg/dL at any time, study physician will be notified to suggest appropriate treatment and ketones will be checked. If ketone

concentration is  $>0.6$  mmol/L, the study team will check the insulin pump infusion site and correction insulin will be administered per study physician judgement via the subject's insulin pump or study-supplied insulin pens. The study team will monitor CGM decay and ketones will be checked every 60 minutes until  $\leq 0.6$  mmol/L.

3. If ketone concentration is  $\geq 3.0$  mmol/L, the study subject will be discontinued, DiAs will be changed to Stopped mode, and appropriate medical treatment will be sought. If the subject is discontinued, he/she may repeat the admission at discretion of the PI.
4. If CGM  $<60$  mg/dL at any time, subjects will be given approximately 16 grams of fast-acting rescue carbohydrates. Study team will monitor CGM rise and will consider treating again if CGM  $<80$  mg/dL after 20 minutes. Hypoglycemic treatments can occur at any time per study physician request.
5. If CGM  $<80$  mg/dL at any time during the exercise session, subjects will suspend the exercise activity and take approximately 8-16 grams of fast-acting rescue carbohydrates. Study team will monitor CGM rise and will consider treating again if CGM  $<80$  mg/dL after 20 minutes. Exercise activity will resume once CGM  $\geq 80$  mg/dL.
6. Prior to the subject being discharged from the admission after either completing the study procedures or discontinuation, the CGM and ketones will be checked. The subject will be discharged once the CGM reading is between 80-250 mg/dL and ketone concentration  $\leq 0.6$  mmol/L.

## **STOPPING RULES**

### **Entire Study**

1. The study will be stopped if two similar AE's occur that result in stopping the study for individual study subjects or if there are system communication failures, which may trigger revision of the system software. The Principal Investigator and Senior DiAs Engineer will evaluate this data and make recommendations concerning continuation, modification, or termination of the trial. Additionally, the Principal Investigator or the IRB-HSR may decide to stop the trial or part of the trial at any time. In this case, the Principal Investigator will promptly inform the subjects and assure appropriate therapy and follow-up. Additionally the Principal Investigator will notify the IRB if the study is temporarily stopped. Early study stop will be documented and the following information will be collected:

1. Date and cause of the ending
2. Description of any serious adverse event leading to the study ending
3. The study may resume if the underlying problem can be corrected by a protocol or system modification that will not invalidate the results obtained prior to suspension. The IRB will be notified if the study is stopped, and permission to resume will be obtained from the IRB prior to restarting.

### **Criteria for stopping the study for an individual subject**

1. The subject may request to be withdrawn (withdrawal of informed consent) from the study at any time for any/no reason. The Principal Investigator, IRB-HSR, or Senior DiAs Engineer may decide to stop the trial or part of the trial at any time. In this case, the Principal Investigator will promptly inform the subject and assure appropriate therapy and follow-up, if needed.
2. A subject who does not complete the protocol may be replaced or rescheduled.
3. If the subject has a positive pregnancy test, she will be stopped.
4. If the subject has a serious adverse event, he/she will be stopped.

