**2. What is the study design?**

This is a single-center randomized crossover trial. We will target completion of 15 adults (age 18-65 years) with Type 1 Diabetes who use an insulin pump. Subjects will undergo an initial Screening Visit and randomization will occur if the visit is successfully completed. After completion of the Screening Visit, each subject will participate in an at home Data Collection Period that will last approximately 14 to 28 days while using their personal insulin pump, a personal glucometer, a study CGM, and a study activity tracker (i.e., Fitbit). This data collection period may be extended to gather more days of quality data, if needed per principal investigator judgement. Once the data has been collected and processed, subjects will participate in two 24-hour admissions (Experimental and Control Admission) in a semi-controlled environment (i.e., hotel), performed in the assigned random order. During both admissions, subjects will use their personal insulin pump and glucometer, and a study CGM. Subjects will be admitted around 9AM. Subjects will be advised to have their home breakfast per their normal routine; around 12PM, they will be provided lunch, followed by an exercise session around 2:30PM. The exercise session will consist of three 15-minute bouts of moderate-intensity exercise (i.e., stationary bicycle). Around 7PM, subjects will be provided a controlled dinner; the SI-informed bolus calculator will be used in the Experimental Admission while standard therapy will be used in the Control Admission. Subjects will then be observed overnight and discharged in the following morning.

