**Subjects- see below**

**1. Provide target # of subjects (at all sites) needed to complete protocol.**

Fifteen (15) subjects are needed to complete the study.

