**2. Describe expected rate of screen failure/dropouts/withdrawals from all sites.**

Because of the length of the study, we expect an approximately 40% rate of dropouts/withdrawals from the study.

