**Study procedures other than those required for subject safety would be stopped during the admissions if:**

- a. The subject has a positive pregnancy test.
- b. The subject had a serious adverse event deemed related to study.
- c. Glucagon is required to treat hypoglycemia.
- d. The subject experiences a seizure.
- e. The subject experiences loss of consciousness.
- f. The subject becomes unable to eat or drink.
- g. The subject develops ketones  $\geq 3.0$  mmol/L.
- h. The subject develops abdominal pain, vomiting illness, fever  $\geq 101.5^{\circ}\text{F}$ , significant illness, or need to use epinephrine or glucocorticoids.

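### Participants stopped for severe events may be replaced to reach 15 completers and no analysis set is defined, so the outcome itself can decide who is in the paired LBGI comparison and Cohen's d

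*Combined protocol and SAP*

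**What the plan says.** **Replacement.** Combined protocol and SAP, Stopping Rules, criteria for an individual subject, item 2: "A subject who does not complete the protocol may be replaced or rescheduled". No exception is made for the reason or the timing.

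**Stops that overlap with the outcome.** Item 4 of the same list: "If the subject has a serious adverse event, he/she will be stopped". The list of events that stop study procedures during an admission includes "Glucagon is required to treat hypoglycemia", "The subject experiences a seizure" and "The subject experiences loss of consciousness", as well as a study-related serious adverse event.

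**Target.** Under study design: "We will target completion of 15 adults (age 18-65 years) with Type 1 Diabetes who use an insulin pump". Under Subjects, question 1: "Fifteen (15) subjects are needed to complete the study". On attrition, question 2: "we expect an approximately 40% rate of dropouts/withdrawals from the study". Up to 25 may enrol.

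**Analysis.** Statistical Considerations, question 4, makes post-dinner LBGI from CGM, Experimental versus Control Admission, the primary analysis. Each participant is their own control. Cohen's d from this trial is to power the main trial. The section gives no analysis population, no rule for an admission that is cut short, and no rule on which attempt counts when an admission is repeated.

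**The concern.** The primary aim is safety and feasibility, with hypoglycemia as the measure. A participant who needs glucagon, has a seizure or loses consciousness from hypoglycemia after the dinner bolus is at the far end of that measure. The same event can end participation. If only completers are analysed, being in the data depends on the result.

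An Experimental-Admission event lost in this way flatters the calculator in the LBGI contrast. A lost Control-Admission event removes evidence in the calculator's favour. The effect size carried into the main trial inherits the selection. Because replacement brings the count back to 15, a reader of the paired result would not see that anyone was missing. Admission order is unblinded, so deciding who counts after the data are in would also be open to influence.

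**Working it through.** **1. The plan's own figure.** 15 / (1 − 0.40) = 25, which matches the stated maximum enrolment. So 25 − 15 = 10 non-completers can be absorbed. The plan does not separate those lost before any study dinner from those stopped after one.

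**2. When a pair is lost.**

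| When the participant stops | What the documents allow |
|---|---|
| Data Collection Period | No dinner data; replacement does not depend on post-dinner LBGI |
| First admission after dinner, no return | At most one LBGI, so no paired difference: loss is forced |
| First admission after dinner, later rescheduled or repeated | A pair is possible, but which attempt counts is not stated |
| Second admission after dinner | Both dinners can have CGM; a pair is possible if data from the stopped admission are used, which is not stated |

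**3. Does replacement cause the bias?** Take the only effect in the documents, the in silico LBGI change from 2.4 to 1.3, a difference of −1.1. Fourteen completers averaging −1.1 give −1.1. Adding a replacement at −1.1 also gives −1.1. The shift comes from leaving the stopped participant out; replacement only restores n.

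**4. Shift in the mean (illustration).** Fifteen at −1.1 plus one stopped participant at x: mean = (15 × (−1.1) + x) / 16. For x = +5, +9 and +15 this is −0.72, −0.47 and −0.09. These x values are assumptions; the documents give none.

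**5. Shift in Cohen's d (illustration).** Step 4 has no spread and so gives no d. The documents give no SD for the paired difference, so s = 1.0 to 3.0 is assumed. Take 14 participants with mean −1.1 and SD s. The fifteenth is either a typical replacement at −1.1, or the stopped participant at −1.1 + ks, with k = 2 or 3 for an Experimental event.

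- Replaced: mean = −1.1; SD = s√(13/14).
- Kept: mean = −1.1 + ks/15; SD = s√[(13 + 14k²/15)/14].
- Main-trial N (paired; 5% two-sided and 80% power, both assumed) = ((1.96 + 0.84)/d)², rounded up.

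| s | \|d\| replaced | \|d\| kept, k = 2 to 3 | Ratio, replaced to kept | N replaced | N kept |
|---|---|---|---|---|---|
| 1.0 | 1.14 | 0.88 to 0.73 | 1.29 to 1.57 | 7 | 11 to 15 |
| 1.5 | 0.76 | 0.55 to 0.43 | 1.39 to 1.76 | 14 | 27 to 43 |
| 2.0 | 0.57 | 0.38 to 0.28 | 1.50 to 2.02 | 25 | 55 to 98 |
| 3.0 | 0.38 | 0.21 to 0.13 | 1.78 to 2.82 | 55 | 173 to 432 |

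At s = 2.0 the 14 without any replacement give |d| = 1.1/2.0 = 0.55. This is close to 0.57 and confirms step 3.

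**6. Control-Admission event (k = −2 or −3).** The ratio of |d| replaced to kept runs from 0.83 to 1.09. Keeping the event moves the mean towards benefit (at s = 2.0, from −1.10 to −1.37 or −1.50) but also raises the SD, so d changes little, or in the opposite direction.

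**The case against.** The strongest reply is that the plan never excludes anyone. A reader might infer that stopped participants are dropped by rule; the documents do not say so, and the gap is silence about the analysis set. CGM is monitored throughout the admission, and the in-admission stops spare procedures needed for safety. Post-dinner data may therefore exist after a stop, at least until discharge. This stands, and it is what makes the fix cheap.

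A reader might also infer that replacement is the source of the bias. Step 3 shows that it is not: a ban on replacement alone would leave the estimate unchanged and reduce n.

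A third tempting reading is that only system or sensor faults permit a return. The list of problems after which a subject may resume names only such faults, but it does not call itself exhaustive. Glycemic Guidelines item 3 lets a participant discontinued for high ketones repeat the admission at the investigator's discretion, and the replacement rule itself mentions rescheduling. The serious-adverse-event stop is the firmer route to a lost pair. These return routes do not close the gap, because the plan does not say which attempt is analysed.

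The study-level rule halts the trial at two similar adverse events that stop individuals. That prevents a run of replaced cases but not a single one. Finally, this is a descriptive pilot, LBGI need not be extreme after a brief treated event, and nothing removes the event from adverse-event records. All of that limits the size of the problem. It does not help the LBGI contrast or d, and d is the stated reason for choosing 15.

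**Conclusion.** The concern holds in a limited form. Replacement for any reason, a target counted in completers, and no analysis set together allow 15 pairs that were selected partly on the outcome. The bias would come from analysing completers only; replacement conceals it.

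It is conditional on the analysis being restricted to completers. The loss is unavoidable only for a first-admission stop without return. Direction depends on the admission in which the event occurs.

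The size cannot be established from the documents. Under the assumed SDs and an assumed Experimental event 2 to 3 SD from the mean, one lost participant inflates |d| by about 1.3 to 2.8 times. A lost Control event gives a ratio of 0.83 to 1.09. A reader might go further and conclude that the trial's safety report would miss the event; the documents do not support that, since only the LBGI comparison and d are affected. The point is worth correcting before any admission data are analysed.

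**What to change.** 1. **Statistical Considerations, question 4.** Define the primary LBGI set as all randomized participants who received a study dinner bolus in either admission. Use CGM from dinner to discharge, including any recorded after study procedures stop. When an admission is repeated or rescheduled (Procedures Related to Discharge item 7; Glycemic Guidelines item 3), take the first attempt as primary.
2. **Same section.** Form the paired difference whenever both admissions have post-dinner CGM. When only one does, report that LBGI and the event by admission type beside the paired result. Give d with and without that participant over a stated range of assumed values.
3. **Individual stopping criteria, item 2.** State that a participant added after someone is stopped following a study dinner bolus is additional to that person in the analysis and report, not a substitute.

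The cost is protocol wording and an extra line in the results table. The figures 15 and 25 stand, no visit or measurement is added, and no clinical stopping or treatment rule changes. The downside is that a few participants may be unpaired and the effect estimate may be less favourable.

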**Study procedures other than those required for subject safety would be stopped during the admissions if:**

- a. The subject has a positive pregnancy test.
- b. The subject had a serious adverse event deemed related to study.
- c. Glucagon is required to treat hypoglycemia.
- d. The subject experiences a seizure.
- e. The subject experiences loss of consciousness.
- f. The subject becomes unable to eat or drink.
- g. The subject develops ketones  $\geq 3.0$  mmol/L.
- h. The subject develops abdominal pain, vomiting illness, fever  $\geq 101.5^{\circ}\text{F}$ , significant illness, or need to use epinephrine or glucocorticoids.

**The subject may resume the study after the following problems are resolved:**

1. Correction of a malfunction of the system or controller once the problem is clearly identified and the system has been repaired
2. Loss of sensor data acquisition for more than three hours
3. If remote monitoring cannot be restored within 180 minutes, study staff will monitor it at least hourly.

[figure not shown]

Figure 3: Diagram of the study research visit

**2. If this protocol involves study treatment, explain how a subject will be transitioned from study treatment when they have completed their participation in the study.**

The optimized bolus calculator will be used during the Experimental Admission (either Visit 3 or Visit 4, according to the randomization). After the Experimental Admission is completed, subjects will resume their usual insulin parameters.

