- 4 Since the visits will be randomized, regardless of when the experimental visit occurs, the MD supervising the trial will look at the standard dose suggested by the DiAs system using the participant's insulin therapy parameters and will indicate that dose (control) if the assigned insulin dose suggested by the SI bolus calculator is deemed to be unsafe. This will be equal regardless of who is the physician supervising the visit. In this way any bias will be avoided since the criteria used by all MDs listed on this protocol will be the same.
- 5 During both visits, control and experimental, the same procedures will be followed. Therefore, the dose suggested by the DiAs system using the participant's insulin therapy parameters during the experimental admission to override the dose suggested by the SI bolus calculator, should be consider safe and usual care for that particular participant.

Visits 3 and 4 will be fully supervised by a research team located at the hotel and gym at all times and will be monitored and supervised by the primary physician. In the event that the primary physician could not be available for a particular visit, the backup MDs will cover. The team will consist of a minimum of one registered nurse (trained in the execution of the protocol as well as in the management of hypo- and hyperglycemia) and a technician (trained in the use and maintenance of the DiAs system). In addition, one of the study medical physicians, primary MD, and one senior engineer will be on call during the entire admission, with backup physicians and engineer available if the primary contact is unable to be reached.

The CGM used in the study is FDA-approved for the non-adjunctive measurement of blood glucose and will be remotely monitored in real-time during the entire admission (including exercise) by the study team via the DiAs Web Monitoring platform. The CGM readings will be the primary source of blood glucose levels. There are no protocol fingerstick blood glucose measurements other than at times of CGM calibration and if directed by the study team.

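### When remote glucose monitoring is lost, no scheduled glucose check is required for at least 180 minutes in an uneventful interval, chiefly sleep after exercise and the dinner bolus

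*Combined protocol and SAP*

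**What the plan says.** The rule on lost remote monitoring is item 3 under the heading on resuming the study, within the Stopping Rules: "If remote monitoring cannot be restored within 180 minutes, study staff will monitor it at least hourly". Item 2 of the same list reads "Loss of sensor data acquisition for more than three hours" and names no backup measurement.

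The routine arrangement is in the section on Visits 3 and 4. CGM is watched remotely through the DiAs web platform for the whole admission. On the source of glucose values the section says "The CGM readings will be the primary source of blood glucose levels", and on fingersticks "There are no protocol fingerstick blood glucose measurements other than at times of CGM calibration and if directed by the study team".

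The Glycemic Guidelines during Research Visit set the action thresholds. Item 4 applies when CGM is below 60 mg/dL: "at any time, subjects will be given approximately 16 grams of fast-acting rescue carbohydrates". Item 2 covers high values: "If CGM >300 mg/dL for more than 1 hour or >400 mg/dL at any time, study physician will be notified".

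Staffing is substantial. The visits are to be "fully supervised by a research team located at the hotel and gym at all times", with at least one registered nurse trained in managing hypo- and hyperglycemia, a technician trained on DiAs, and a physician and senior engineer on call with backups. For the night, the study design section says "Subjects will then be observed overnight and discharged in the following morning".

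**The concern.** The treatment thresholds work only if someone sees a glucose value. The routine means of seeing one is the remote link, and the one rule for its failure starts substitute monitoring only after three hours. Participants are told to go to sleep at about 10:00PM, after afternoon exercise chosen to alter insulin sensitivity and a dinner bolus at about 7:00PM. Watching a sleeping participant does not yield a glucose value.

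The sponsor's own simulation of this scenario (Background) counted 34 hypoglycemia treatments with the standard bolus and 6 with the SI-informed bolus in the 6 hours after dinner. These are simulated counts, but they show that lows in this window are anticipated. What is at stake is the safety of participants in both admissions.

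**Working it through.** No sample-size or error-rate formula applies, and the plan gives no figure to reproduce. The check is a reading of every admission-day glucose duty, followed by clock arithmetic.

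**1. Which duties call for a glucose value during an outage?**

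| Duty | Where | When it calls for a value | Covers uneventful sleep? |
|---|---|---|---|
| Meal and correction boluses based on CGM | Procedures during Research Visit, item 9 | At a bolus | No |
| Dinner bolus formula uses current glucose | Background | About 7:00PM | No |
| Exercise rule at 80 mg/dL | Glycemic Guidelines, item 5 | During exercise | No |
| Follow-up after a treated low, 20 minutes | Glycemic Guidelines, item 4 | After a low has been seen | No |
| Discharge check | Glycemic Guidelines, item 6 | About 9:00AM | No |
| Fingersticks for calibration or at staff discretion | Procedures during Research Visit, item 10 | If needed, prompted or chosen | Not required |
| Supervision, overnight observation, accompanying staff member | Visits 3 and 4; Study design; Procedures, item 13 | No glucose interval given | Not specified |
| Remote monitoring throughout | Procedures during Research Visit, item 14 | Continuous | This is the function that has failed |
| Substitute staff monitoring | Resume list, item 3 | At least hourly, after 180 minutes | Yes, but only then |

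The criteria for stopping procedures during an admission do not mention lost monitoring. No section sets a stricter rule for the night.

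**2. Length of the interval with no scheduled check.** Assume that the 180 minutes run from the start of the loss; the text does not say.

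- First substitute check exactly at 180 minutes: gap = 180 minutes.
- First check at the end of the first hour of hourly monitoring: gap = 180 + 60 = 240 minutes.

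**3. Where it falls on the clock.**

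- Loss at 10:00PM: 10:00PM + 180 minutes = 1:00AM; 10:00PM + 240 minutes = 2:00AM.
- Measured from a 7:00PM dinner, the gap runs from hour 3 to hour 6, or to hour 7.

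**4. Against the protocol's own intervals.**

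- The re-check after a treated low is at 20 minutes: 180 / 20 = 9 times longer.
- The trigger for CGM >300 mg/dL is persistence beyond 60 minutes: 180 / 60 = 3 times longer.

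**5. Effect of removing the wait.** With checks at 0, 60 and 120 minutes after the loss is recognised:

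- scheduled checks before 180 minutes: 3 instead of 0 (4 if the one at 180 minutes is counted);
- longest interval between scheduled checks: 60 minutes instead of 180 to 240.

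**The case against.** The strongest reply is that the text leaves far less unprotected than item 3 alone suggests.

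- **Event-driven values.** A reader might infer that no glucose value of any kind is required in the first 180 minutes of an outage. The documents do not support that: boluses, exercise, follow-up of a treated low and discharge all still call for CGM. The gap is confined to uneventful intervals. This part of the reply stands.
- **Link versus sensor.** The web platform and the Bluetooth connection from CGM to DiAs (Procedures at beginning of Research Visit, item 4) are separate. Losing the former does not by itself remove local readings, and the thresholds still apply to a working CGM. This also stands, but no one is required to read the device locally at any interval.
- **Staff on site.** A reader might infer that participants are left unwatched for three hours. They are not, and staff may take a fingerstick whenever they choose. This lowers the risk. It does not turn a choice into a scheduled check.
- **Drafting.** Item 3 is a misplaced sentence with an undefined object, and it does not expressly suspend the whole-admission monitoring duty. True. But it is the only outage rule staff would find. If its object were the link rather than glucose, no fallback glucose check would be specified at all, so the reading used here is the more favourable one.
- **Choice of interval.** The documents do not settle whether hourly is right; every 15 to 30 minutes after dinner and overnight could also be argued. Hourly is proposed because it is the protocol's own fallback interval.

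**Conclusion.** The point holds in a limited form. In an uneventful interval during loss of remote monitoring, chiefly sleep after about 10:00PM, the plan requires no scheduled glucose check for at least 180 minutes and possibly about 240, while requiring action on CGM <60 mg/dL whenever it occurs. For sensor-data loss, the resume list names no backup measurement.

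This rests on three readings: the undefined object of item 3 is glucose, the 180 minutes run from the start of the loss, and the upper figure depends on how hourly checking is applied. It describes what the wording allows, not what is expected with trained staff present. The documents give no outage frequency, so no risk can be estimated.

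A reader might also infer that the LBGI comparison is affected. The documents do not support this: the rule is the same in both admissions, and a lost remote display does not in itself mean lost sensor data. The change is a minor improvement in participant safety.

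**What to change.** Delete the 180-minute wait and move the rule from the resume list to the Glycemic Guidelines during Research Visit, for both admissions. Suggested text:

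> On recognising loss of remote monitoring or of sensor data, on-site staff will obtain a glucose value at once and then at least every hour until it is restored. The value will be a local CGM reading if only the remote link is down, and a fingerstick if sensor data are lost. Checks will be more frequent if the study physician directs.

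This also states what is being monitored and how. The three-hour criterion in item 2 can stay as a condition for resuming the study.

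The cost is a short wording change. Staff, the study CGM and the participant's glucometer are already on site. An outage of up to 180 minutes would bring 3 extra checks, or 4 counting one at 180 minutes. If sensor data are lost these are fingersticks, and some may wake the participant.
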